5.4 SUMMARY OF PRIOR CLINICAL EXPERIENCE AND SAFETY

5.4.1 INXN-1001 and INXN-2001

No clinical studies of INXN-1001 in combination with INXN-2001 have been previously performed.

Please refer to the current Investigator's Brochure for additional information regarding the previous nonclinical and clinical experience with INXN-1001 and INXN-2001.

[REDACTED]

[REDACTED]

5.4.2 Adenovirus Safety

Adenoviral vectors have been used extensively to deliver a variety of gene products to human subjects including cancer patients. Although adenoviral vectors are immunogenic, and virtually all recipients have pre-existing humoral immunity to adenoviruses, they are generally considered to be a safe, well tolerated method of gene delivery that results in minimal side effects in patients.

In a Phase I/II clinical trial in prostate cancer (PCa), direct intraprostatic injection of a replication-defective adenovirus vector encoding bacterial nitroreductase (dose levels 5×10^{10} - 1×10^{12} virus particles), the vector was well tolerated, with minimal side effects, and had a short half-life in the circulation.²⁸ Numerous studies have utilized adenoviral vectors to deliver the p53 gene via the intratumoral route. Oral leukoplakia patients who were given multiple intraepithelial injections of recombinant adenovirus (rAd)-p53 (1×10^8 virus particles/cm²) did not demonstrate signs of dose-limiting toxicity, and administration of the (rAd)-p53 was well tolerated.²⁹ No dose-limiting toxicity was observed in chemoradiation-resistant advanced esophageal carcinoma patients receiving intratumoral injections of adenovirus containing p53 (10×10^{11} particles to 25×10^{11} particles).³⁰ Adverse events attributed to Ad.5CMV-p53 treatment were generally mild to moderate, with the most common AEs being Grade 1 or 2 fever (100 % of patients) and local pain (30% of patients.) Three patients displayed hyperglycemia that was attributed to nutrition, two patients showed hypocalcemia, and one patient each experienced partial thromboplastin time elongation or an increase in serum amylase or creatinine.³⁰ No other significant laboratory abnormalities were detected on follow-up evaluations.

An adenoviral vector encoding hIL-12 has been studied using intratumoral injection in patients with advanced digestive malignancies, at doses up to 3×10^{12} viral particles, and was well tolerated. Common AEs were similar to symptoms observed with gene delivery by other adenoviral vectors, including transient, mild to moderate fever, malaise, sweating, and lymphopenia.³¹

5.4.3 Safety of Intratumoral injection of IL-12 genes

In comparison with administration of recombinant IL-12 protein, injection of plasmids or adenovirus containing hIL-12 genes to cancer patients has proven to limit or abrogate the toxic effects of hIL-12, thus providing an effective way to provide this potent immunomodulatory cytokine. This has been observed in Phase I and II clinical trials where IL-12 is delivered locally, IL-12 levels have been measured systemically in patient serum, and in the majority of these studies, increases in IL-12 serum levels post baseline have not been observed.³¹⁻³³ Numerous studies have shown gene delivery of IL-12 to be well tolerated. In a Phase I dose escalation trial using electroporation to administer plasmid DNA encoding hIL-12 into metastatic melanoma, minimal systemic toxicity and no IL-12-related adverse events were observed in subjects treated at several dose levels.³⁴ Similarly, intratumoral injection of a plasmid DNA encoding human IL-12 (2 to 20 mg of total DNA) in subjects with melanoma was also well tolerated.³⁵ Limited elevations in serum cytokines were observed after treatment. Intra-peritoneal injection of hIL-12 plasmid DNA formulated in polyethyleneglycol-polyethyleneimine-cholesterol (PPC) given to women with chemotherapy-resistant recurrent ovarian cancer also was found to be generally safe and well tolerated. Low-grade fever and abdominal pain were the most common side effects.³⁶ Plasmid DNA was not detected in the patients' serum samples and treatment-related increases in IFN- γ levels were observed only in pleural fluid but not in serum. Similar findings have been obtained with intratumoral injection of adenoviral vectors encoding hIL-12 at doses ranging from 2.5×10^{10} to 3×10^{12} viral particles, to subjects with advanced pancreatic, colorectal, or primary liver malignancies.³¹ Treatment was well tolerated and dose-limiting toxicity was not reached. AEs were transient, with fever, malaise, sweating, and lymphopenia being the most common AEs observed. No cumulative toxicity was observed. All AEs were deemed to be related to injection of the virus and not to transgene expression.

5.5 RATIONALE FOR STUDY DESIGN AND DOSE SELECTION

The objectives of this Phase I/II clinical trial are to assess the safety, objective response rate, and immunological and biological effects of intratumoral injections of INXN-2001 in combination with escalating dose levels of oral INXN-1001. The dose escalation portion of the study (Phase I) uses a standard 3+3 design commonly used in Phase I studies of investigational anticancer therapies. To provide an opportunity to monitor the safety of the combination therapy, there will be at least 7 days between the initiation of treatment for the sentinel (first) subject and additional subjects in all cohorts during the dose escalation stage of the study. Phase II will be enrolled (approximately 15 subjects) at or below the MTD and using two groups. One group will receive an INXN-1001 daily for 7 days dosing regimen, and the other group will receive an every other day dosing regimen for 14 days to compare tolerability of INXN-1001 at the 160-mg dose.

Phase I: In each of six 21-day cycles, the subjects will receive one intratumoral injection of INXN-2001 in combination with 7 oral daily doses of INXN-1001.

Phase II, Group 1: In each of six 21-day cycles, the subjects will receive one intratumoral injection of INXN-2001 in combination with 7 oral daily doses of INXN-1001.

Phase II, Group 2: In each of six 28-day cycles, the subjects will receive one intratumoral injection of INXN-2001 in combination with 7 oral doses of INXN-1001 administered every other day for 14 days.

The INXN-1001 dose levels to be studied (5 to 160 mg/day) are within the range of doses administered in previous human clinical trials [REDACTED] and are expected to provide plasma levels that are biologically effective for [REDACTED] activation. Although good safety and tolerability is expected based on previous clinical experience, rigorous safety monitoring during the course of this study will be performed by the Safety Review Committee (SRC).

In all treatment cycles throughout the study, the INXN-2001 dose will be fixed [REDACTED] dose. This dose was selected based on: (i) preclinical studies that indicated that this would be within an effective range, and (ii) previous clinical trials of administered adenoviral vectors [REDACTED]

During the conduct of this study, in addition to monitoring of safety and therapeutic efficacy, tumor tissue and peripheral blood samples will be studied for indications of immunological and biological effects, with a particular attention to markers of IL-12 gene expression and levels of specific anti-melanoma T cell immunity. The combined clinical and laboratory data will be studied to assess for INXN-1001 dose-response relationships and to aid in identifying a recommended dose level for further study.

The population for study was selected as those with unresectable Stage III or IV melanoma, which is rarely curable with standard therapy and who are therefore considered to be appropriate candidates for clinical trials exploring new forms of treatment.³⁷ Because melanomas are responsive to immunotherapeutic approaches (see [Section 5.1](#) Disease Background), this subject population may potentially benefit from investigational therapy with INXN-2001.

6. STUDY OBJECTIVES AND DESIGN

6.1 OBJECTIVES

The primary objective is to:

- Evaluate the safety and tolerability of intratumoral injections of INXN-2001 (Ad-RTS-hIL-12) in combination with INXN-1001 (activator ligand) in subjects with unresectable Stage III or IV melanoma.

The secondary objectives are to:

- Inform the selection of an INXN-1001 dose(s) and regimen for further study in combination with INXN-2001.
- Assess preliminary anti-tumor activity according to RECIST 1.1 criteria.

- Assess anti-tumor response based on total measurable tumor burden.
- Evaluate the immunological effect of study treatment in terms of cellular and humoral immune responses, as well as other biological activities in the injected tumor(s), tumor-involved draining lymph nodes (if accessible) and in the peripheral circulation.
- Evaluate the extent of the uptake of INXN-2001 into tumor cells and tumor-infiltrating immune cells, and to assess adenoviral vector shedding in body fluids.
- Assess the pharmacokinetics (PK) of INXN-1001 in subjects with unresectable stage III or IV melanoma.

6.2 STUDY DESIGN AND DOSE ESCALATION PROCEDURE

6.2.1 Overall Study Design

This is a single-arm, open label, Phase I/II dose escalation study of intratumoral injections of INXN-2001 and oral INXN-1001 in subjects with unresectable Stage III or IV melanoma.

Phase I: Four sequential dose escalation cohorts of INXN-1001 in combination with a fixed dose of INXN-2001 are planned. Subject enrollment and dose escalation will proceed according to a standard 3+3 design. Each subject will be treated for up to 6 treatment cycles, each 21 days in duration. Previously enrolled subjects received 3 cycles under former versions of this protocol. There will be at least 7 days between the initiation of treatment for the sentinel (first) subject and additional subjects in all cohorts during the dose escalation stage of the study. In each cycle, subjects will be treated with one intratumoral injection of INXN-2001 in combination with 7 oral daily doses of INXN-1001. No intrasubject dose escalation will be allowed.

Phase II: Approximately 15 subjects will be enrolled in Phase II at or below the MTD. For Group 1, in each of six 21-day cycles, the subjects will receive one intratumoral injection of INXN-2001 in combination with 7 oral daily doses of INXN-1001. For Group 2, in each of six 28-day cycles, the subjects will receive one intratumoral injection of INXN-2001 in combination with 7 oral doses of INXN-1001 administered every other day for 14 days.

Safety and tolerability will be assessed by the incidence and severity of adverse events as determined by NCI Common Terminology Criteria for Adverse Events (CTCAE) v4.03. A SRC comprised of the Medical Monitor, Principal Investigators, and sponsor representatives, will be convened to review safety information and to decide upon dose escalation and further subject enrollment.

The anti-tumor activity of study treatment will be assessed according to RECIST v1.1 guidelines. Additional assessment of anti-tumor activity will be explored based on total measurable tumor burden.³⁹ ([Appendix 4](#))

Immunological and biological markers of response will include examinations of tumor biopsy samples, cytokine levels, PBMCs and antibody response to INXN-2001.

6.2.2 Treatment Parameters and Duration

All subjects will receive intratumoral injections of INXN-2001 [REDACTED] on Day 1 of each cycle. The subjects will also receive an oral daily dose of INXN-1001 for 7 consecutive days (Phase I and Phase II Group 1) or every other day for 14 days (Phase II Group 2) starting on Day 1 of each cycle.

Subjects may receive up to 6 cycles of study treatment. Because tumor nodules may enlarge due to the anticipated induction of an inflammatory response, subjects with disease progression (per RECIST criteria) may still complete the 6 treatment cycles, unless the progression is clinically significant, eg, development of new metastases or an ECOG performance status that increases during study treatment to ≥ 2 .

6.2.3 Safety Review Committee (SRC)

A SRC comprised of the Medical Monitor, Principal Investigators and sponsor representatives, will hold periodic teleconferences to evaluate the safety and treatment status of all subjects. The SRC will review and assess the safety data at the completion of each dose cohort as described in Section 6.2.6, and at any other time as needed. The SRC has the authority to recommend dose modifications for safety concerns.

A written summary documenting the results and recommendations of each review will be provided to the Investigator(s) and maintained on file with the sponsor. Additional sub-Investigators and personnel may participate in reviews as indicated.

In Phase I, following a cohort review, the SRC may recommend proceeding with enrollment in the next dose cohort, enrolling additional subjects in the current cohort, dropping back to a lower cohort, exploring an alternate dose level, or not enrolling any additional subjects. The dose escalation and enrollment guidelines outlined in [Section 6.2.6](#), as well as the study stopping rules outlined in [Section 6.2.7](#), will be used as the basis for these assessments.

In Phase II, Group 2, the DLT definitions in [Section 6.2.4](#) will be utilized along with the criteria for de-escalation. The SRC may recommend a dose reduction for subjects in Group 2 if one or more DLT(s) are observed.

While the SRC is expected to reach a consensus opinion regarding any premature discontinuation or significant modification of the study, the sponsor may independently stop the study.

6.2.4 Definition and Management of Dose-Limiting Toxicity (DLT)

Dose-limiting toxicity (DLT) is defined as:

- Any injection site reaction that includes ulceration, necrosis, severe tissue damage or where operative intervention is required.
- Any local or systemic injection reaction that has life-threatening consequences, requires urgent intervention or results in death.

- Any study drug-related \geq Grade 3 adverse event, except nausea and/or vomiting in subjects who did not receive optimal treatment with anti-emetics.

Phase I and Phase II, Group 1: If DLTs have been observed in >1 of the 3-6 subjects in a cohort during the first treatment cycle, the MTD will have been exceeded and further use of that dose will be discontinued in all subjects, and the next lower dose cohort will be assessed as to whether it meets the definition of the MTD.

Phase II, Group 2: If an adverse event that meets the Phase I DLT definition is observed in >1 of the 3-6 subjects in Group 2 during the first treatment cycle, the SRC will convene to discuss reduction in dose and/or change to posology and the cohort will be expanded by 3 subjects. The recommended Phase II dose will be the dosage and posology where ≤ 1 of 3 to 6 subjects experiences an adverse event as described in the definition of DLT.

The Medical Monitor should be immediately notified of any potential DLT. Subjects will be withdrawn from study treatment if they experience an injection site reaction that meets DLT criteria or other Grade 3 toxicity related to study drug that, upon review of the SRC, is deemed to be a DLT. If, however, the subject has experienced a substantial benefit from treatment and the SRC recommends continuation on the study, re-exposure to the experimental treatment may proceed at a lower dose of INXN-1001 on a case by case basis. Any subject who experiences a Grade 4 toxicity related to study treatment will be withdrawn from study.

6.2.5 Definition of Maximum Tolerated Dose (MTD) and Recommended Phase II Dose (RP2D)

The MTD will be defined as the highest dose of INXN-1001 studied in combination with INXN-2001 at which a DLT has been seen in a maximum of 1 in 6 subjects ($< 33\%$) during the first treatment cycle. Subsequent to Cycle 1, study drug-related adverse events that meet the DLT criteria will also be considered by the SRC and any previous determination of the MTD may be reconsidered.

The recommended Phase II dose will be the dosage and posology where ≤ 1 of 3 to 6 subjects experiences an adverse event as described in the definition of DLT.

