6.2.7 Study Stopping Rules

Rules for stopping dose escalation due to DLTs observed during the first cycle of study treatment are outlined in [Section 6.2.4](#). In the event that a given dose is determined to have exceeded the MTD, then further use of that dose will be discontinued for all subjects as noted in [Section 6.2.4](#). Subsequent to Cycle 1, study drug-related adverse events that meet the DLT criteria will also be considered by the SRC and any previous determination of the MTD may be reconsidered.

Stopping rules for toxicities that occur from Day 1, Cycle 2 through the Post-treatment follow-up visit will apply as follows:

- If an adverse event can be definitely shown to be unrelated to study treatment (eg, motor vehicle accident, bee sting, elective surgery), that specific toxicity will not be considered in a stop vs. dose modification decision.
- Recruitment in the current dose level will not be stopped for Grade 2 (NCI CTCAE v.4.03) non-dose limiting toxicities, irrespective of the number of events or number of subjects.
- Recruitment in the current dose level will be stopped for any Grade 4 toxicity. Upon occurrence, all data will be reviewed by the Investigator, the Investigator's IRB as applicable, ZIOPHARM Medical and Regulatory Staff, and the SRC to determine if the study should proceed and if/what changes must be implemented.
 - For toxicity based on laboratory tests: an abnormality related to study drug per investigator assessment must be confirmed (when appropriate) by repeat testing before qualifying for review as above.
- Subject enrollment into the study will be halted in the event of any study drug-related death. In this case, subject enrollment will only resume following review and approval of the SRC.

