Dose Escalation Plan During Phase I	
Phase I: Four sequential INXN-1001 dose escalation cohorts are planned, as described in Table 1. Subject enrollment and dose escalation will proceed according to a standard 3+3 design. No intrasubject dose escalation will be allowed. An intermediate dose level(s) of INXN-1001 may be explored after review of all available safety and activity data, as may be decided by the SRC.
 
Initially, 3 subjects will be enrolled into each sequential dose cohort, beginning with the lowest planned INXN-1001 dose level.
 
Dose escalation will not occur until the third subject in a cohort has completed the first treatment cycle (7 days of oral activator ligand followed by 14 days of observation). Following this, a meeting of the SRC will be convened to review all reported \geqGrade 3 adverse events to determine if these meet dose-limiting toxicity (DLT) criteria. In addition, the SRC will review the overall occurrence of adverse events and relevant laboratory data in each cohort to determine whether the MTD has been reached. Following this review, the SRC will advise on subject enrollment, dose escalation and/or cohort expansion using the following guidelines:
 
a) If 0 of 3 subjects in a cohort experiences a DLT, then the next higher dose-level cohort may be enrolled.b) If 1 of 3 subjects in a cohort experiences a DLT, then up to 3 additional subjects will be enrolled into that cohort.c) If >1 of 3-6 subjects in a cohort experience a DLT, then enrollment into that cohort will cease, and the previous dose-level will be explored as the maximum tolerated dose (MTD). A total of 6 subjects will be enrolled into this lower-dose cohort, including previously enrolled subjects. Using the same criteria, lower-dose cohorts will be explored as the MTD until ≤ 1 of 6 subjects experience a DLT.d) Intermediate INXN-1001 dose levels may be recommended by the SRC (i) to advance the INXN-1001 dose in a smaller increment than originally planned, or (ii) to better determine the MTD. The intermediate dose level(s) will not exceed the higher of either a dose level in which >1 of 3 or 6 subjects experienced a DLT or the highest planned dose level (ie, Cohort 4, 160 mg/day). If 160 mg is the MTD and pharmacokinetic data suggests that higher dose(s) of INXN-1001 are indicated, then additional dose cohorts may be explored following an approved amendment of this protocol.
--	--

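### The RP2D definition accepts 1 DLT in 3 where the MTD definition allows at most 1 in 6 in Cycle 1, the enrolment halts leave a Cycle 1 gap, and no planned table isolates Cycle 1 DLTs

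*Protocol*

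**What the plan says.** **Dose definitions.** Protocol 6.2.5 makes the MTD the highest INXN-1001 dose at which "a DLT has been seen in a maximum of 1 in 6 subjects", glossed as under 33% and counted in the first cycle. The RP2D is the dose and schedule at which no more than 1 "of 3 to 6 subjects experiences an adverse event as described in the definition of DLT". That sentence also appears in 6.2.4 for Phase II Group 2. It has no minimum of 6 and names no cycle, although its place in 6.2.4, straight after a rule about Cycle 1, may imply one.

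**What follows one DLT in three.** In Phase I, Appendix 5 says: "If 1 of 3 subjects in a cohort experiences a DLT, then up to 3 additional subjects will be enrolled into that cohort". In Group 2, 6.2.4 fixes a response only when more than 1 of 3 to 6 subjects has a DLT in Cycle 1; then "the SRC will convene to discuss reduction in dose and/or change to posology and the cohort will be expanded by 3 subjects". Below that, 6.2.3 gives discretion: "The SRC may recommend a dose reduction for subjects in Group 2 if one or more DLT(s) are observed".

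**Enrolment halts.** For Cycle 1, 6.2.7 points to the DLT count in 6.2.4. Its bullets include a recruitment stop for Grade 4 toxicity and this rule: "Subject enrollment into the study will be halted in the event of any study drug-related death". They stand under the lead-in "Stopping rules for toxicities that occur from Day 1, Cycle 2 through the Post-treatment follow-up visit will apply as follows".

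**Reporting.** SAP 12.2 puts one row for dose-limiting toxicities in the overall adverse event summary (Table 14.3.2.1). It has no cycle limit, and percentages are taken over all patients in each dose cohort, by phase and group. The exposure listing (SAP 12.1) flags each patient with a DLT, and the injection reaction listing gives DLT status with dates. No DLT-evaluable set is defined, although protocol 7.4 allows replacement of subjects who leave before completing Cycle 1 dosing.

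**The concern.** Safety is the primary objective, and informing the choice of INXN-1001 dose and regimen is the first secondary objective. Read literally, the protocol has two standards for an acceptable dose, and they disagree at exactly 1 DLT in 3 subjects. Group 2, which introduced the every-other-day schedule, has no required response at that result.

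The halt rules have a similar weakness. Cycle 1 is the first exposure to the combination, yet the automatic halts are worded to begin one cycle later.

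The reporting matters most now. The MTD definition uses a Cycle 1 rate, and no planned table shows that rate by regimen. A reader of the report may be unable to tell from the tables whether a regimen met the protocol's own criterion.

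**Working it through.** **1. The plan's own threshold.** 1/6 = 16.7%, which is under 33%. The first excluded result, 2/6 = 33.3%, is not. So the MTD gloss is consistent with its count. But 1/3 = 33.3% passes the RP2D wording and fails the MTD gloss.

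**2. How far the rules differ.** The documents give no DLT rates, so p, the true Cycle 1 rate, is assumed, and patients are taken as independent.

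- Exactly 1 of 3: 3p(1−p)²
- At least one more DLT in the next 3: 1−(1−p)³
- Pass at most 1 of 3: (1−p)³ + 3p(1−p)²
- Pass standard 3+3: (1−p)³ + 3p(1−p)²·(1−p)³
- Pass at most 1 of 6: (1−p)⁶ + 6p(1−p)⁵

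| p | exactly 1 of 3 | further DLT in next 3 | pass ≤1 of 3 | pass 3+3 | pass ≤1 of 6 |
|---|---|---|---|---|---|
| 0.20 | 0.384 | 0.488 | 0.896 | 0.709 | 0.655 |
| 0.30 | 0.441 | 0.657 | 0.784 | 0.494 | 0.420 |
| 0.40 | 0.432 | 0.784 | 0.648 | 0.309 | 0.233 |
| 0.50 | 0.375 | 0.875 | 0.500 | 0.172 | 0.109 |

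Worked at p = 0.40: ≤1 of 3 is 0.216 + 0.432 = 0.648; 3+3 is 0.216 + 0.432 × 0.216 = 0.309. The ≤1 of 3 column applies only if a regimen is accepted at 3 subjects.

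**3. Size of the halt gap.** Let g be the assumed Cycle 1 rate of related Grade 4 or 5 events. Among the 15 planned Phase II subjects, the chance of at least one is 1−(1−g)¹⁵:

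- g = 0.01: 0.140
- g = 0.02: 0.261
- g = 0.05: 0.537
- g = 0.10: 0.794

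In a Phase I cohort of 3, exactly one such event and no other DLT has probability 3g(1−g−o)², where o, the share of patients with another DLT, runs from 0 to 0.2:

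- g = 0.01: 0.029 to 0.019
- g = 0.02: 0.058 to 0.037
- g = 0.05: 0.135 to 0.084
- g = 0.10: 0.243 to 0.147

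All of these are upper bounds on the gap, because injection-associated events are not taken out.

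**4. What the SAP row can show.** Treated numbers (SAP 1.0):

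- Phase I: 3, 3, 3 and 4, total 13
- Phase II Group 1: 4
- Phase II Group 2: 4 + 3 + 2 = 9
- Phase II total: 4 + 9 = 13

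No single-regimen column reaches 6. The Group 2 column (9) and the two Overall columns (13 each) do, but they mix regimens. 160 mg daily is split across phases, 4 + 4 = 8. Phase I 160 mg has 4 treated patients, neither 3 nor 6, so the DLT denominator is not evident.

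If 0 or 1 patients in a cohort had a DLT in any cycle, the Cycle 1 count cannot exceed 1 and the row is enough to place it within the limit. With 2 or more, the row cannot separate Cycle 1 from later cycles. 80 mg every other day has 2 patients, below even the 3 in the RP2D wording.

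**The case against.** **On the RP2D.** Phase II is limited to doses at or below the MTD (Synopsis; 6.2.1; 6.2.6), so the RP2D sentence cannot carry the dose above it. About 15 Phase II subjects were planned, so enrolment would normally pass 3. The missing cycle window is not itself lenient, since counting every cycle is stricter. All of this stands. What remains is the smaller denominator, with no fixed response at 1 of 3, on a schedule that the escalation did not test.

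A reader might infer that the lenient rule was used. The documents do not support that. SAP 1.0 and 4.4 say the dose was reduced because of DLTs at both 160 and 120 mg every other day. That was within the SRC's discretion, and no DLT counts are given.

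**On the halts.** A reader might infer that no single Cycle 1 Grade 4 event or death carries a mandatory halt. That goes too far:

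- Protocol 8.2.7, Table 3, stops enrolment for a fatal injection reaction. The text after it applies the stopping rules to injection-associated events that cannot be shown to be unrelated to INXN-2001. Neither names a cycle, and an injection is given on Day 1 of every cycle.
- Section 6.2.3 makes 6.2.7 a basis for Phase I cohort reviews, which Appendix 5 holds after the third subject's first cycle.

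Both refer back to a section whose lead-in starts at Cycle 2, so the text is ambiguous there. It is clearly silent only for Cycle 1 events not associated with the injection. Other Cycle 1 protections exist: immediate Medical Monitor notice, withdrawal of the subject with a related Grade 4 event, SRC review at any time, and the sponsor's power to stop. The 7-day gap between the "sentinel (first) subject and additional subjects in all cohorts during the dose escalation stage of the study" does not extend to Phase II. None of these is an automatic enrolment halt.

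**On the SAP.** It would be wrong to say that DLTs are not tabulated by cohort; they are. With 26 patients, the listings should let a reader find the Cycle 1 events, and the SRC documents its reviews in writing. That makes the table cheap rather than unnecessary, because the criterion rate would otherwise have to be assembled by hand.

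**Conclusion.** The point holds in three limited parts.

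1. The RP2D and MTD definitions conflict at 1 DLT in 3. At assumed DLT rates of 20 to 50%, between 38% and 44% of three-subject cohorts land on that result. Three more subjects would then show a further DLT in 49 to 88% of those.
2. The halts leave a clear Cycle 1 gap for Grade 4 events and drug-related deaths that are not injection-associated; for the rest the wording is ambiguous. At assumed event rates of 1 to 10%, at most 14 to 79% of trials with 15 Phase II subjects would see a relevant event.
3. The SAP row does not show the Cycle 1 rate where 2 or more patients in a cohort had a DLT. The data exist in listings.

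All event rates are assumptions. Enrolment is reported as finished, so parts 1 and 2 matter for an amendment or reuse and cannot change past exposure. Part 3 can still be acted on. Because it bears on the primary objective and costs little, it should be fixed before the report is written.

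**What to change.** **For this trial.** Add one descriptive table of Cycle 1 DLTs by regimen, over DLT-evaluable patients (those who completed Cycle 1 or had a DLT in it). Show 160 mg daily for Phase I, for Group 1 and pooled, and show later-cycle DLTs separately. In the clinical study report, state whether any regimen met the MTD or the RP2D definition.

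**For the protocol text, if amended or reused.** Require at most 1 of 6 in Cycle 1 for the RP2D, with 1 of 3 leading to expansion in Group 2 as in Phase I. Keep SRC review of later-cycle DLTs. Apply the Grade 4 and drug-related-death halts from the first dose.

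**Cost.** One table for 26 patients from data already collected, and one sentence in the report. The report may have to say that no regimen formally met the definition. The stricter RP2D rule would also pass fewer tolerable regimens: at a true DLT rate of 20%, 71% under 3+3 or 66% under at most 1 of 6, instead of 90%.
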